| TCAQ | Thought Control Ability Questionnaire |
| ТМҒ | Trial Master File |
| TMG | Trial Management Group |
| TSC | Trial Steering Committee |

- **USM** Urgent Safety Measure
- VABS Vineland Adaptive Behaviour Scales
- **WAIS-III** Wechsler Adult Intelligence Scale

BCI intervention in ASD V1.0, 24.06.15

1 Amendment History

| Amendment No. | Protocol version no. | Date issued | Author(s) of changes | Details of changes made |
|------------------|----------------------------|----------------|-------------------------|-------------------------|
| | V 1.0 | | | |

2 Synopsis

| Short title | BCI (Brain Computer Interface) Intervention in Autism (BCIAUT) |
|--|---|
| Acronym | BCIAUT |
| Internal ref. no. | IBILI - VB - 2015 – 01 |
| Study design | SINGLE ARM WITHIN – SUBJECT "BEFORE-AFTER" DESIGN. |
| Trial/study participants | ASD (experimental) |
| Planned sample size | 15 (plus 3 in case of drop outs) |
| Follow-up duration | 6 months after last intervention session |
| Planned trial/study | 4 months |
| period | |
| period Primary objective | Increase the number/rate of responses to initiation/response to joint attention cues in a serious game |
| period Primary objective Secondary objectives | Increase the number/rate of responses to initiation/response to joint attention cues in a serious game Improve general social cognition functions |
| period Primary objective Secondary objectives Primary endpoint | Increase the number/rate of responses to initiation/response to joint attention cues in a serious game Improve general social cognition functions Number/rate of responses to initiation/response to joint attention cues |
| period Primary objective Secondary objectives Primary endpoint Secondary endpoints | Increase the number/rate of responses to initiation/response to joint attention cues in a serious game Improve general social cognition functions Number/rate of responses to initiation/response to joint attention cues ATEC, Vineland Scores |

3 Study summary & schema

3.1 Study schema

3.2 Participant flow diagram

Clinical trial: Improving social attention in ASD: a BCI approach

3.3 Study summary

Clinical research has demonstrated that ASD children have deficits in the interpretation of others' intentions from gaze-direction or other social attention cues (Baron-Cohen, Baldwin, & Crowson, 1997; Baron-Cohen, 1989).

The purpose of the study is to investigate whether a brain computer interface (BCI) using electroencephalographic (EEG) signals can be used to train social cognition skills (in particular interpretation of gaze direction pointing to objects of interest) in ASD patients and whether this improves clinical symptoms.

The intervention comprises seven BCI sessions spread over four months. The first four sessions are planned to occur weekly, and the rest monthly. In each session, the subject is asked to identify objects of interest based on the gaze direction of an avatar. The subject response is interpreted from the EEG signal (using the P300 component, as established in our previous work).

4 Introduction

4.1 Background

Autism Spectrum Disorder and Joint Attention

Autism spectrum disorder (ASD) is a severe, early-onset and life-long neurodevelopmental disorder with a high worldwide prevalence and a distribution of four males (M) to one female (F) (Baron-Cohen et al., 2009; Fombonne, 2003; Oliveira et al., 2007). ASD is characterized by deficits in social interaction and communication as well as by a repetitive pattern of behaviour and interests (American Psychiatric Association, 2013).

Joint attention is an early-developing social communication skill defined by the coordination of attention of two individuals towards a third object or event (Bakeman & Adamson, 1984). This skill is critical in the development of language and communication abilities later in life, and people with ASD show severe deficits in joint attention abilities.

Clinical research studies proved that ASD children show a deficit in interpreting others intentions from gaze-direction (Baron-Cohen et al., 1997; Baron-Cohen, 1989). ASD subjects also demonstrated a lack of attentional modulation in a fMRI study especially evident for social stimuli (Bird, Catmur, Silani, Frith, & Frith, 2006). Other studies suggest that ASD patients may have deficits in the cognitive processing of social stimuli: impairments in exogenous orienting of attention to social cues but not to objects (Leekam & Moore, 2001) and reduced saliency of social stimuli/preference for non-social stimuli (Dawson et al., 2004; Klin, 2002; Swettenham et al., 1998). Altogether, this inability means they are unable to predict or understand other people's actions suggesting dysfunctional social behaviours.

Gaming and Intervention Strategies

ASD subjects often experience discomfort with unpredictable social environments (Charlop-Christy, Le, & Freeman, 2000). The use of computerized intervention enables the development of skills in a highly standardized, predictable, consistent and controlled environment. Simultaneously, it allows individuals to work at their own pace and ability level (Golan & Baron-Cohen, 2006). This is a crucial point for this population. For many years the use of technology in ASD intervention relied primarily on the use of videotapes for instructional video modelling (Bellini & Akullian, 2007), but now the potential of technology extends far beyond simple video modelling to areas such as interactive computer programs and virtual reality.

Individuals with ASD often have relatively strong visual processing skills and a preference towards electronic media, thus it is likely that the dissemination of intervention via computer technology would be particularly appropriate and motivating for these individuals (Shane & Albert, 2008). An interesting and updated review about the use of innovative computer technology for the development of social skills to individuals (Wainer & Ingersoll, 2011) reveals the promising potential of this kind of approach, in particular if realistic scenes are used. The studies mentioned in this review reported significant improvements in the social skills addressed, but, altogether, some studies did not verify the transfer of these skills to more realistic and meaningful contexts. In the field of joint attention, some other studies have explored methods for systematically teaching joint attention to children with autism (Jones, Carr, & Feeley, 2006; Koegel, Vernon, & Koegel, 2009; Whalen, Schreibman, & Ingersoll, 2006).

These studies included embedding motivating social interactions into the intervention which effectively improved childrens' social areas. However, the infrequent implementation of the protocols compromised the carryover after the end of the interventions.

Brain-Computer Interfaces, Electroencephalography and the P300 signal

The EEG P300 oddball signal is a well-known neural signature of attention processes for detection of rare items in a series of distinct stimuli types. It has been classically reported as an enhanced positive-going component with a latency of about 300 milliseconds and a normal scalp distribution over the midline electrodes (for a review see Duncan et al., 2009; Patel & Azzam, 2005; Polich, 2007). P300 based oddball paradigms are often used in BCI which are systems that allow individuals to communicate without having to use verbal or motor means of communication (Blankertz et al., 2010; Farwell & Donchin, 1988; Kleih et al., 2011; Mak et al., 2011; Wolpaw & Wolpaw, 2012). P300 can be identified even at single-trial level (high signal-to-noise ratio) allowing good communication speeds for BCIs.

4.2 Rationale for current study

The main hypothesis is that training of initiation and response to joint attention cues using gaming/BCI interfaces can be used to improve joint attention social cognition skills in ASD participants.

The BCI setup will be used to train initiation and repeated responses to a joint attention object. An independent game platform will be used to test whether enhanced rates of joint attention (initiation and responses) were achieved.

This study aims to demonstrate that improvements in identification of social cues (and improvement of overall social behaviour) in subjects with ASD can be achieved using social games together with a BCI setup. The primary goal is to ensure increased rate of responses to joint attention cues.

To evaluate the improvements, we will use a new task/realistic game that will challenge the detection of initiation of joint attention cues (from avatars – gaze or pointing). The number of correct responses (to particular objects and not to non-object parts of the scene, will be recorded). We will also record incorrect responses to non-pointing body gestures. Participants will be challenged with about 20 events per minute (one every three seconds), of variable degree of difficulty. Given that the experiment lasts 10 minutes, and some events are control measures, we will have a total of 150 test events and 50 control events. We expect that ASD subjects will be able to correctly report a mean of 75 of the target events, based on tailored task difficulty.

Considering the longitudinal design proposed, with alpha 0.05, power of 80%, and standardized effect of 0.8 (improvement of 8 points for an estimated SD of 10 points) we would need 15 subjects. We will consider three additional subjects to account for drop-offs. The sample size calculations were performed based on a matched 2 sided paired t-test. To determine these values we used the G*Power tool (Faul, Erdfelder, Lang, & Buchner, 2007). The sample size calculations were performed under the assumption that the distribution of the mean differences is normal. Without the normality assumption, we would also need 15 subjects, considering a non-parametric Wilcoxon test.

The structure proposed for this study is the following: (1) initial eligibility screening, (2) preintervention, (3) intervention process, (4) post-intervention, and (5) follow-up.

5 Study objective(s)

5.1 **Primary objective(s)**

Improvement of social attention skills (training joint attention mechanisms) by increasing the rate of responses to joint attention cues. We expect that ASD subjects will be able to increase the number of target events correctly reported, based on a tailored task difficulty.

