10.5 Adherence

Adherence is defined as attending all seven BCI sessions.

After the enrolment, the participant will be given a schedule with the sessions plan. Additionally, the participant or caregiver will be reminded of each session by telephone-call one week earlier and by message the day before.

On the basis of following the study protocol, follow-up plan should depend on specific situation of participants such as avoiding the holiday or the inconvenient day. When the intervention is over, researchers should remind patients of the next appointment time. For eventual absent participants, researchers should do telephone interviews in time, ask the reason and try to reschedule.

11 Outcome measures

11.1 **Primary outcome measure**

The results [Number of items of social attention that a patient can accurately identify in the avatar's action, e.g. looking at, pointing at] in a separate "Joint-attention task" will be the primary outcome measure. The experimental group will be evaluated in the pre and post evaluation time with this test.

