13.2 Sample size

Considering the longitudinal design proposed, with alpha 0.05, power of 80%, and standardized effect of 0.8 (improvement of 8 points for and estimated SD of 10 points) we would need 15 subjects (plus 3 in case of drop outs). We will add three additional subjects to account for drop-offs. The sample size calculations were performed based on a matched 2 sided paired t-test. To determine these values we used the G*Power tool (Faul et al., 2007). The sample size calculations were performed under the assumption that the distribution of the mean differences is normal. Similarly, without the normality assumption, we would also need 15 subjects, considering a non-parametric Wilcoxon test.

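### The scored baseline of the joint-attention game appears to be participants' first contact with it, so learning the game would count as improvement; an identical unscored practice run before each scored run would reduce this cheaply.

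*Protocol*

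**What the plan says.** The primary outcome is the number of social attention items correctly identified in a joint-attention task that is separate from the BCI training (Protocol 11.1, SAP 6.2.1). Protocol 4.2 introduces it: "To evaluate the improvements, we will use a new task/realistic game that will challenge the detection of initiation of joint attention cues". On its pace the same section says "Participants will be challenged with about 20 events per minute (one every three seconds), of variable degree of difficulty". A run takes 10 minutes. For the number of events, the section states: "we will have a total of 150 test events and 50 control events". Participants are expected to "correctly report a mean of 75 of the target events, based on tailored task difficulty".

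On timing, Protocol 11.1 states: "The experimental group will be evaluated in the pre and post evaluation time with this test". Protocol 10.3 puts these assessments at week 0 and week 16. SAP 3.6 and 6.2.2 add the follow-up. Protocol 12.3 goes from the diagnostic and neuropsychological evaluation straight to the joint-attention test.

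The design is single arm (Protocol 6). Protocol 15.1 tests the mean paired difference against zero with a two-sided paired t-test. Protocol 13.2 plans for an "improvement of 8 points for and estimated SD of 10 points", giving 15 participants. SAP 6.3.2, 6.3.5 and 6.5 mark covariate adjustment, sensitivity analyses and additional analyses as not applicable.

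Neither document mentions a practice or familiarisation run, a second baseline, parallel forms or test-retest data for this task. The pilot study in Protocol 12.1 concerns the BCI training task.

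**The concern.** An event about every three seconds in an unfamiliar game asks participants to learn the controls and the pace while they are being scored. If the first attempt is the scored baseline, part of any later gain may be familiarity with the game rather than better joint attention. Both push the score upwards.

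In a randomised trial a control group would show the same familiarity gain, and it would cancel. Here nothing cancels it: there is one arm, the null value is exactly zero, and no analysis allows for practice. The follow-up assessment does not help, because it is simply a third exposure. Protocol 6 classes the endpoint as efficacy and SAP 3.4 describes the main outcomes as testing for superiority, so a significant change would be read as benefit from the training.

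**Working it through.** **Inputs**
- Target change 8 points, SD 10, two-sided alpha 0.05, paired t-test (Protocol 4.2 and 13.2).
- The SD is that of the paired differences, because SAP 3.3 defines the effect size as Cohen's dz.
- 150 scored events per assessment, expected mean 75 correct (Protocol 4.2).
- Practice gain g: not in the documents. Assumed to be 2, 3 or 4 points (a quarter to a half of the 8-point target) and to persist to week 16.

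**Step 1. The plan's own figure.** For a paired t-test the noncentrality is dz × √n, with n − 1 degrees of freedom. With dz = 8/10 = 0.8, exact power is 82.1% at n = 15 and 79.0% at n = 14. The planned 15 reproduces.

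**Step 2. How small a change is significant.** The smallest significant mean change is t(0.975; 14) × SD/√n = 2.145 × 10/√15 = 5.5 points. That is 5.5/150, or under 4% of the scored events.

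**Step 3. Practice gain with no training effect.** Put dz = g/10 and take the probability that t exceeds 2.145, that is, rejection in the direction of improvement.

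| Assumed gain g | dz | Noncentrality, dz × √15 | Declared improvement |
|---|---|---|---|
| 0 | 0 | 0 | 2.5% |
| 2 | 0.2 | 0.77 | 11% |
| 3 | 0.3 | 1.16 | 19% |
| 4 | 0.4 | 1.55 | 30% |

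**Step 4. Would a second scored run per visit solve it?** Averaging two runs is a natural companion proposal, so it was checked. With independent events of equal difficulty, chance variance is 150 × 0.5 × 0.5 = 37.5 before and 150 × (83/150) × (67/150) = 37.1 after. The difference therefore has chance variance 74.6, out of the assumed 10² = 100. If difficulty is strongly mixed, so that average p(1 − p) is 0.15 instead of 0.25, this falls to 0.6 × 74.6 = 44.7.

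Two runs halve the chance part, removing 22 to 37 of the 100:
- equal difficulty: SD = √(100 − 37.3) = 7.92, power 95% at n = 15;
- mixed difficulty: SD = √(100 − 22.35) = 8.81, power 90% at n = 15.

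Two caveats follow.
- The gain depends on the planning SD. If the SD of differences were 15, with the same chance variance, power would move only from 49% to 53–56%.
- Less noise makes a remaining practice gain easier to declare significant. A gain of 3 points with no training effect goes from 19% to 23% (SD 8.81) or 28% (SD 7.92).

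**The case against.** The strongest reply is that the premises rest on silence. No section says that the task is played once per visit or that the scored baseline is first contact. The word new may mean only that the game is separate from the BCI training game. Protocol 4.2 and 5.1 refer to tailored task difficulty, which might involve some calibration contact, and the study schema is not shown in the text. This stands: the point is about what the plan describes, not about what the site may in fact do.

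Second, the practice gain is assumed, and it would have to survive 16 weeks after a single 10-minute exposure. This also stands. The percentages show what follows if a gain exists and lasts; they do not show that it does. A reader might infer that a positive result would be false, or that the error rate is known to be inflated. The documents support neither.

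Third, a warm-up at baseline only would make the visits unequal: baseline scored warm and later visits scored cold could bias against the intervention. This is right, and the remedy has to be identical at each visit.

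Fourth, the study is partly a feasibility study and meets its own power target. That limits how much extra testing can be asked for, but a short practice run remains proportionate for the primary outcome.

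**Conclusion.** The point holds as a weakness in how the primary outcome is measured. As written, the plan gives no protection against first-exposure learning in a design that would count it as benefit. Under assumed gains of 2, 3 or 4 points lasting to week 16, with n = 15 and an SD of differences of 10, improvement would be declared in 11%, 19% or 30% of trials with no training effect, against 2.5%.

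Three stronger readings are not supported.
- The sample size is not in error: 15 reproduces, with 82% power.
- Chance variation between events, up to about three quarters of the assumed variance, is not all avoidable. Two runs would remove about 22–37% of the assumed variance, and the 90–95% power holds only if the SD of differences really is 10.
- Familiarisation does not make the result attributable to training. It reduces practice effects, but a single arm with repeat testing cannot separate the two.

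**What to change.** In Protocol 11.1, 12.3 and 12.4 and SAP 6.2.2, specify:
1. one unscored familiarisation run immediately before the scored run, done in the same way at baseline, session 7 and follow-up;
2. task difficulty fixed across visits for each participant, with any calibration step described;
3. a statement that this reduces practice effects but cannot separate them from the effect of training without a control group.

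If a practice or calibration run already takes place, describe it and apply it identically at every visit.

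The cost is about 10 extra minutes per visit and some fatigue, with no new equipment, staff or participants. A second scored run per visit is best left out. If it is wanted, it should be optional and used only together with the familiarisation run, because on its own it makes a practice gain easier to declare significant.

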5.2 Secondary objectives

Improvements in general aspects of social cognition (as measured by neuropsychological tests) derived from a generalization of the skills learned.

6 Study design

| Patient Information according to eligibility criteria | Intervention - 7 sessions (4 months) Intervention - 7 sessions (4 months) BCI session BCI session C |
|---|---|
| | Image: Signed state sta |

Allocation: not applicable

Endpoint Classification: Efficacy Study

Intervention Model: Single arm

Primary Purpose: Basic Science and clinical feasibility study

Participants: 15 ASD subjects (plus 3 in case of drop outs)

7 Participant selection

The eligible patients for the study should be high functioning ASD adolescents and adults. These participants should also meet all the following inclusion criteria and none of the exclusion criteria. All queries about patient eligibility should be directed to [name] before registration.

7.1 Inclusion criteria

- Positive diagnostic results for ASD in:
 - Autism Diagnostic Interview-Revised;
 - Autism Diagnostic Observation Schedule;
 - The Diagnostic and Statistical Manual of Mental Disorders, Fifth Edition (DSM-5) criteria.

7.2 Exclusion criteria

- Global Intelligence Quotient < 80
- Associated medical condition such as epilepsy, neurocutaneous or other genetic syndromes, or other usual comorbidity in ASD samples

8 Recruitment

8.1 Number of participants

A total of 15 (plus 3 in case of drop outs) participants will be recruited. We expect to recruit one subject each three weeks. The study is expected to start on the second semester of 2015 and last up to 82 weeks (including follow-up).

8.2 **Recruitment process**

Participants will be recruited from the National Clinical Program for ASD at University of Coimbra. The Lead Researcher is responsible for contacting the participants.

8.3 Informed consent

Informed Consent can be found attached in the appendices. This Informed Consent must be signed by each participant/legal representative before the beginning of the study.

8.4 Screening logs

The data related to screening logs (paper format) will be kept in a secured room only accessible by BRAINTRAIN researchers. Additionally, data required to support analysis of the study will be entered and stored in an MS SQL Server database hosted on servers at Cardiff University. The hosting server is on a locked, secure machine room at Cardiff University.

The database will be backed up daily and access to the database will be via secure logon (username and password) and restricted to named study personnel only, as detailed in the study's PRA log. Each study will only see data and actions relating to their own study.

9 Withdrawal & loss to follow-up

Participants have the right to withdraw consent for participation in any aspect of the BCI intervention at any time. The participant's care will not be affected at any time by declining to participate or withdrawing from the study.

If a participant initially consents but subsequently withdraws from the study, clear distinction must be made as to what aspect of the study the participant is withdrawing from. These aspects could be:

- Withdrawal from study intervention
- Withdrawal from study follow-up
- Withdrawal from entire study and does not want data to be used.

A patient may withdraw or be withdrawn from the intervention for the following reasons:

- Withdrawal of consent for intervention by the participant
- Any alteration in the participants condition or circumstances which justifies the discontinuation of the intervention in the Investigators' opinion

In all instances participants who consent and subsequently withdraw should complete a withdrawal form or the withdrawal form should be completed on the participant's behalf by the researcher/clinician based on information provided by the participant.

10 Intervention

10.1 **EEG**

During the EEG acquisition, researchers will stay in the same room as participants. Researchers will be able to see and monitor participant's behaviour and their performance. The acquisition can be stopped at any time, should participants' request this or researchers become concerned about participant's health.

